9. DATA COLLECTION AND MEASUREMENTS

9.1. Overview of measures, instrument and data sources

Table 3 summarizes the measures (with references to the standard instruments) we will use and the timing of data collection aimed at minimizing participant burden. Data will be collected using 4 methods: online surveys, home scale, medical record review, and Medicaid claims data.

Measures and Instruments	Data source(s)	Timing				
		BL	36-38wk	2 mo	4 mo	6 mo
Demographics, preferred language, acculturation, & medical history ^{58,59}	Online (+ phone assisted) surveys	x				
Discrimination experiences ⁶⁰	Online (+ phone assisted) surveys	x				
Postpartum weight retention (PPWR)	Pre-pregnancy height & weight (prior to 15 wks) from medical records	x				
Gestational weight gain (GWG)	37-weeks & postpartum weights from home scale		x	x	x	x
Safety net services & home visiting care utilization and experiences	Online (+ phone assisted) surveys	x	x	x	x	x
Maternal health care utilization	Claims + Online (+ phone assisted) surveys		x	x	x	x
Health behaviors (diet ^{61,62} ; physical activity ⁶³ ; alcohol, marijuana, tobacco use ⁵⁸ ; breastfeeding ⁶⁴)	Online (+ phone assisted) surveys	x	x	x	x	x
Maternal wellness (depression ⁶⁵ , stress ⁶⁶ , sleep ⁶⁷ , social supports ⁶⁸)	Online (+ phone assisted) surveys	x	x	x	x	x
Infant weight and length (birth weight and 2, 4, and 6 months weights)	Online (+ phone assisted) surveys & medical records			x	x	x
Infant health care utilization	Claims + Online (+ phone assisted) surveys			x	x	x

Abbreviations: BL=baseline; mo=months postpartum; wk=weeks gestation.

9.2. Medical record review

“Baseline pregnancy” weight will be defined as the earliest measured weight in prenatal care obtained from prenatal medical records. We will also abstract height, blood pressure and comorbid conditions from medical records. Participants will consent to prenatal and infant medical record release during the consent process. [Most of our participants will not be Johns Hopkins patients. For the few participants who are Johns Hopkins patients, following consent to review medical records, the study team will access medical records via the Epic for manual data extraction of height, weight, and comorbid conditions. We will not be submitting a CCDA request. For all non Johns Hopkins patients, we will be requesting their medical records directly from their prenatal care provider via secure fax or secure email.](#)

9.2. Assessment of maternal weight using the Home Scale

Maternal weights (measured at 37-weeks, 2 months, 4 months, and 6 months postpartum) will be measured in light indoor clothes without shoes and recorded by a home **study scale** (BodyTrace or a similar product) and recorded and transmitted to the study team automatically using cellular connectivity (no WIFI or cellular plan required). The scale will be delivered to the participant's home upon enrollment. The cellular enabled scales provide valid weight measures and have been used by several large-scale weight interventions⁶⁹.

9.3. Online Questionnaires, administered using REDCap – in English and Spanish languages

We have designed questionnaires using standard instruments (Table 3). Questionnaires were selected to minimize participant burden and enable completion at home.

9.3.1 Demographics, family characteristics and acculturation

We will collect maternal, infant and family health and demographic characteristics using standard surveys from CDC Pregnancy Risk Assessment Monitoring Survey (PRAMS).^{53,54}

9.3.2 Smoking, Marijuana, and Alcohol

We will assess smoking, marijuana, and alcohol use using the PRAMS.^{53,54}

9.3.3 Utilization of care

We will assess utilization of care using questions from PRAMS.^{53,54}

9.3.4 Dietary Intake

We will assess dietary intake using the NHANES 2009-10 Dietary Screener Questionnaire (DSQ) Eating Habits Questionnaire⁶¹, fast food frequency using the Coronary Artery Risk Development in Young Adults (CARDIA) Study questionnaires and sugar sweetened beverage intake using the NHANES questions⁶¹.

9.3.5 Physical Activity

We will assess physical activity using the International Physical Activity Questionnaire – Short Self-Administered Format⁶³.

9.3.6 Women's Wellness and Mood

We will assess women's wellness through measures assessing mental health, social support, perceived stress, and sleep quality. We will assess depression and anxiety using the Edinburgh Postpartum Depression scale⁶⁵, which we modified to remove the question on suicidality. We will assess perceived stress using the Perceived Stress Scale and Social Support will be measured using the Medical Outcomes Study Social Support Questionnaire⁶⁸. Sleep quality will be measured using the Pittsburgh Sleep Quality Index⁶⁷.

9.3.7 Breastfeeding Practices and Infant health

We will use several questions from the standard and core measures of the CDC Pregnancy Risk Assessment Monitoring Survey (PRAMS), including use of community and safety net programs, pregnancy intention, usual source of care and infant overall health⁵⁸. We also use the PRAMS to breastfeeding intention during pregnancy. We will assess ongoing lactation

practices after delivery (2, 4 and 6 months) using standardized measures from the CDC-Infant Feeding Practices Survey [64](#).

9.3.8. Racial Discrimination

We will assess discrimination using the 6-item short form discrimination scale [70](#).

9.3.10. Home visiting service utilization; Safety net services and home visiting care utilization and experiences

We will ask participants about their utilization of safety net services (i.e., Supplemental Nutrition Program for Women, Infants, and Children, Supplemental Nutrition Program). We will ask about the frequency of and satisfaction with home visiting services.

9.3.11. Satisfaction Survey with the H42-HV Intervention Components

We will assess satisfaction with Health Coaching, Mobile Phone tracking, web-based platform by participants and providers at study completion using a survey tool our team has designed and tested.

9.4. Medicaid claims data. We will request and obtain a data extract of Maryland Medicaid data for all consented participants to assess maternal and infant healthcare utilization outcomes (i.e., attendance at prenatal care visits, postpartum OBGYN visit, primary care visits, infant visits, receipt of infant vaccines). We will have a data use agreement with the Maryland department of health.

10. QUALITY ASSURANCE AND QUALITY CONTROL

Quality Assurance pertains to activities that promote collection of high-quality data, and Quality Control refers to activities that detect emerging data issues with sufficient time to implement appropriate corrective actions. Our approach to Quality Assurance includes: 1) preparing manuals of operations; 2) implementing a master trainer model to train and certify other staff; 3) train and certify all data collectors and recertify data collectors at least annually; 4) maintain logs of certified staff and equipment.

Our approach to Quality Control includes: 1) monitoring counts of completed data collection items through automatic flags in database; 2) running routine reports for missing surveys and flagging unusual data values and data inconsistencies for possible correction measures; 3) reviewing types and distribution of data entry errors/issues and remedying any systematic concerns; and 4) adjusting data inconsistency by endpoint assessment committee to decide possible action and documenting decision made for any data correction prepare reports for staff, investigators and NIMHD and the Safety Officer on Quality Control (see Data Safety and Monitoring Plan).

11. RANDOMIZATION AND BLINDING/MASKING

400 participants will be randomized 1:1 to H42-HV or the mHIP-HV comparator arm. Randomization will be stratified by home visiting site, BMI (BMI ≥ 30 kg/m² vs. 25-30 kg/m²), and gestational age at enrollment, and within each stratum using randomly varying block sizes of 2, 4, and 6. The study's Lead Biostatistician will generate the randomization schedule.

Blinding: Due to the nature of the lifestyle intervention, participants and home visitors and intervention team will not be blinded to randomization assignment. Data collectors will be blinded to assignment. Until the end of the trial all non-intervention team study co-investigators will also remain blinded, except the Lead Biostatistician.

12. INTERVENTION – HEALTHY FOR TWO-HOME VISITING (H42-HV)

12.1. Overview of the H42-HV Intervention components (Table 4)

The intervention draws upon the strengths of preeminent theories from other behavioral weight loss and CVD risk reduction trials [12,71,72](#), including social cognitive theory and behavioral self-management concepts [73,74](#), enhanced by the application of our health coaching framework called COACH. H42-HV employs behavioral strategies such as goal setting, self-monitoring, problem solving and identification of strengths for overcoming barriers utilizing a patient-centered approach. Health coaches will be trained in motivational interviewing, an evidence-based approach aimed at enhancing participants’ intrinsic motivation to change their health behaviors, including diet and exercise, and sleep and stress/time management, and to allow for the personalized and adaptive nature of the intervention [75,76,77](#).

Table 4 describes the three components of the H42-HV intervention: 1) Health Coaching Calls; 2) Online Platform for Learning Activities and Goal Setting Functions; 3) Tracking of health behaviors (diet, exercise), and 4) Self-weighing (weekly). The overarching behavioral goals of the intervention are for participants to have lower postpartum weight retention at 6 months after delivery. Weight and behavioral goals will be promoted through the COACH Framework, a behavioral model guiding coaching calls, behavioral tracking targets and learning activities. Coaches will refer to home visitors for additional support and community resources, based on an established protocol.

Table 4. H42-HV Description and Approach	
COACH Framework to promote weight goals & CMD prevention	Commitment to self, baby and program Omission of high salt/high sugar foods Addition of vegetables + exercise Communication with coach, home visitor Honor yourself through wellness, self-care
Components of program	
Health coaching	Training in patient-centered motivational interviewing approach with supervision by Health Coach Managers (with individualized case management) Starts as late as 33-weeks gestation to 6 months postpartum Phone or video contacts (~20 mins) ~7 in pregnancy/~6 PP
Interactive online learning platform	Learning activities focus on nutrition education, behavior change strategies, wellness (e.g. sleep, mood), long-term CMD prevention; English and Spanish versions
Health behavior tracking	Tracking of diet and exercise (via mobile app or paper/pencil)
Weekly self-weighing	Weekly self-weighing at home on BodyTrace scale
Cardiometabolic risk reduction - Behavioral Goals	
Smoking	Smoking cessation; Avoid second-hand smoke exposure
Pregnancy weight	Within recommended total weight gain 78
Postpartum	Weight: Lose 2% pre-pregnancy, based on pre-pregnancy BMI was ≥ 25.0 kg/m ² 79 Care: Transition to primary care 37 Promote breastfeeding 80
Physical activity	≥ 150 min/week walking (or other moderate exercise)
Diet	↓ fast/junk foods with salt, added sugar, ↑ fruit/vegetables, using DASH Diet and MyPlate principles 81
Role of Home Visitors and Home Visiting Program	

Supportive role, community resource	Facilitate intervention adherence, including contacts and behavioral goals, i.e. may include healthy shopping, postpartum + primary care appointment and pediatric appointment attendance.
--	--

12.1.a. Telephone health coaching calls by trained health coaches. Calls start at enrollment, as early in pregnancy as possible (latest start will be 33-weeks gestation) through 6 months postpartum. Although coaching calls will occur by phone (~20 mins), when possible, some coach contact could occur at the time of home visits in person, or via video interface.

12.1.b. Online interactive Learning Activities. Our literacy adaptation ensured Learning Activities are at $\leq 5^{\text{th}}$ grade reading level. All activities are being translated into Spanish and culturally adapted to create a parallel program. Online learning activities contain embedded images (people and settings) that reflect the diversity of our target population, examples of activities that are readily available in the community and maximize the use of white space, large text and simple graphics to enhance readability and accessibility of the educational content. We enhanced the platform to enable an interactive goal-setting functionality for participants to set health goals paced with their Learning Activities and calls. The online program is maintained and monitored by the study's health coach managers.

12.1.c. Health behavior tracking (diet and exercise). Participants will receive specific skill-building on how to track diet and exercise behaviors via mainstream mobile app or paper/pencil, using procedures from our current trial. Coaches will be able to discuss tracking data with participants. Mainstream tracking apps are available in both Spanish and English.

Table 5. Example checklist for home visitors to support intervention participants
Web-based educational learning activities
Completes Learning Activities
Health coaching communication
Establishes communication with Health Coach
Completes coach contacts
Technology access
Access to device (tablet or phone)
Able to log-in to mobile tracker
Able to log-in to web-based program
Has data plan enabling access to programs
Health behavior tracking (via mobile app or paper/pencil)
Self-weighs at least once per week
Tracked 1 or more food item in last 3 days
Individual Goals & Knowledge (change weekly)
Knows pregnancy weight gain goals
Knows exercise goals
Knows diet goals
Identifies barriers to healthy eating and exercise
Assess barriers to healthful eating goals
Assess barriers to exercise goals

12.1.d Weekly self-weighing. Participants will be asked to weigh themselves weekly at home using their study scale.

12.1.e. Support from home visitors. In collaboration with our home visiting program partners we designed the role of the home visitors to be aligned with the procedures they already use in their program and visits. Because home visitors routinely complete “checklists” for a variety of health topics during home visits, we designed a H42-HV checklist for the home visitors (**Table 5**).

Home visitors will receive training on the program and use of a checklist that involves tasks within their scope of work focused on reaching intervention and behavioral goals and aimed at identifying and addressing social determinants of health. A Home Visiting Coach Manager will ensure appropriate supervision of health coaches, reporting and task completion. Coaches will reach out to home visitors when participants miss coach calls, when participants need help with community

resources and referrals (e.g., food assistance applications, identifying places to purchase healthy food, and finding appropriate exercise options)⁵⁵, or if they require additional assistance problem solving. For example, home visitors could help participants problem solve where to keep the home scale so they remember to use it weekly but to avoid younger children playing with. Or, if a participant sets a goal with the health coach to reduce intake of sugar-sweetened beverages, the home visitor can help them identify low/no-sugar beverage alternatives that are available in their local store.

12.2. Fidelity of the intervention

We will use methods similar to those used in complex, team-based behavioral interventions^{82,83}, to examine fidelity and the relationship with the outcome of PPWR. We will evaluate health coaching intervention fidelity and engage in an iterative quality assurance process. To ensure consistent approaches by health coaches, we will use “Coach Leader Guides” for each coach call (a detailed outline, i.e., review tracking information; review learning materials and discuss successes, barriers, goals). We will also randomly sample coach calls to audio record them for the intervention lead to review and monitor for fidelity. Coaches will ask permission to audio-record at the beginning of a given call and participants will be able to decline at any time. The audio recording will not be analyzed for research or published in any way. All audio recordings will be uploaded to a secure folder and destroyed when the study is completed.

We will ask participants if they would be willing to have a study team member contact them by phone or email when they have completed the health coaching intervention to get feedback on the program. This phone call will be optional and audio recorded if the participant gives permission. Participant feedback will be used to improve the health coaching program in the future.

13.0. Comparison group: Usual home visiting plus (mHIP-HV). Upon randomization, women assigned to Usual Home Visiting Plus [maintain health in pregnancy (mHIP-HV)] will receive usual home visiting services, per agency guidelines and requirements. In addition, we will provide access to a brief video on maternal warning signs educational video that is available in English or Spanish. The video was developed for a home visiting client audience and is publicly available, <https://mdmom.org/warningsigns>. All home visitors, including those for participants in the Usual Home Visiting Plus Care group, will receive the same trainings, including content in Table 5.

14.0 DISCONTINUATION AND WITHDRAWAL OF PARTICIPANTS

Participants who discontinue the study early will be asked to complete remaining assessments at the time of discontinuation, if feasible and acceptable to the participant. All reasons for discontinuation will be documented clearly in study records

14.1. Discontinuation of study

An investigator may discontinue a participant from the study for the following reasons:

- Home visiting program staff, study investigators or Study Safety Officer does not think participation is in the participant's best interest or might be harmful;
- Significant study intervention non-compliance or disruptive behavior (e.g., argumentative with study staff or coach);
- Study is stopped;
- There may be other reasons to that we do not know at this time.

For pregnant women who experience a stillborn or intrauterine fetal demise, we will assess whether she would like to continue in the program, transitioning to the postpartum phase of data collection and/or intervention. Participants will not be discontinued if they choose to have baby adopted.

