14.2. Withdrawal from Study

Participants who sign the informed consent form, and are randomized and subsequently withdraw, or are withdrawn or discontinued from the study, will not be replaced.

Participants are free to withdraw from participation in the study at any time upon request. They will be documented as: "withdrawn by participant" or "withdrawn by study PI". Data collected until the point of withdrawal can still be included in analysis, using the intention-to-treat (ITT) approach.

Participant withdrawal will be documented as a Protocol Event and reason will be documented as a NOTE TO FILE form.

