15. DATA ANALYSIS

15.1 General Approaches

Compare the effectiveness of the H42-HV program using a remotely-delivered health coaching intervention integrated into home visiting with mHIP-HV among 400 pregnant and postpartum women enrolled from early home visiting programs in Maryland:

- Primary outcome: PPWR at 6 months after delivery
- Maternal secondary outcomes: GWG (37 week minus baseline pregnancy [≤ 15 week gestation] weight); Proportion with excessive GWG.
- Infant secondary outcomes: Weight at birth, 2 months, 4 months, and 6 months of age will be gathered as maternal self-report via online surveys and verified with infant medical records.
- Maternal and infant health care utilization, including receipt of postpartum care, ER visits and routine well infant visits, captured for those participants who are Medicaid recipients using claims data.
- Other outcomes: Maternal health behaviors (diet, physical activity, and breastfeeding); Maternal wellness (depression, sleep, and stress)

The main analyses for the primary and secondary outcomes will follow the ITT principle. The analysis for PPWR will utilize a mixed effects model to assess between group difference in mean of total PPWR.

15.2. Main analytic model for the primary outcome of PPWR (difference between pre-pregnancy weight and weight at 6 months postpartum).

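### Participants may be discontinued from the whole study for intervention non-compliance, a ground that bears mainly on the H42-HV arm, and no section clearly keeps their scheduled 6-month weight

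*Combined protocol and SAP*

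**What the plan says.** Section 14.1 (Discontinuation of study) opens with "An investigator may discontinue a participant from the study for the following reasons". One listed reason is "Significant study intervention non-compliance or disruptive behavior (e.g., argumentative with study staff or coach"; another is that participation is not in the participant's "best interest or might be harmful". The power is discretionary, and the text does not define when non-compliance becomes significant. For a fetal loss, the same section separates follow-up from treatment: the woman may continue by "transitioning to the postpartum phase of data collection and/or intervention". It draws no such distinction for non-compliance.

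Three other places bear on what happens next.

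- Section 14.0: "Participants who discontinue the study early will be asked to complete remaining assessments at the time of discontinuation", where feasible and acceptable to her. It adds: "All reasons for discontinuation will be documented clearly in study records".
- Section 14.2 (Withdrawal from Study): "Data collected until the point of withdrawal can still be included in analysis, using the intention-to-treat (ITT) approach".
- Section 15.1: "The main analyses for the primary and secondary outcomes will follow the ITT principle". Section 15.2 fits a mixed model to all available weights from all randomised women.

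The primary outcome, in the other section 14.1 (Primary Outcome), uses the study-scale weight at 6 months after delivery. Section 16.0 assumes that dropout is missing at random.

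**The concern.** Adherence demands differ sharply by arm. Section 12.1 and Table 4 give H42-HV women about 13 coach contacts (about 7 in pregnancy and 6 postpartum), learning activities, behaviour tracking and weekly self-weighing. Section 5.2.3 gives the comparison arm usual home visiting plus a video of under 5 minutes. Removal for intervention non-compliance can therefore occur mainly in one arm.

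If a removed woman's 6-month weight is not sought, it is missing because of her adherence. Adherence may be related to weight in ways that her earlier weights do not capture. That sits badly with the intention-to-treat aim and strains the missing-at-random assumption. If removed women would have retained more weight than their observed data predict, the comparison shifts in favour of H42-HV. If they would have retained less, it shifts against.

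**Working it through.** **Step 1. Do the passages keep the 6-month weight?**

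- Section 14.0, on its more natural reading, brings assessments forward to the day of discontinuation. A weight taken then, possibly during pregnancy, is not the 6-month value. The sentence could also be read as a request, made on that day, for the later assessments.
- Section 14.2 is permissive and covers only data collected before withdrawal.
- Sections 15.1 and 15.2 govern how data are analysed. Keeping a woman in the model with a missing 6-month value is not the same as weighing her.

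So no section clearly keeps the weight.

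**Step 2. Reproduce the plan's figures (section 16.0, Table 6).** 360 × 0.70 = 252, or 126 per arm. The minimum detectable difference is SD × √(2/126) × (1.960 + 1.282), which gives 2.25, 2.86, 3.27 and 3.59 kg for SDs of 5.5, 7.0, 8.0 and 8.8 kg. The noncentral t version gives 2.255, 2.870, 3.280 and 3.608 kg, against the stated 2.26, 2.87, 3.28 and 3.61. Table 6 is reproduced.

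**Step 3. Illustration.** The documents give neither a removal rate nor a weight difference, so these inputs are assumptions:

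- SD 7 kg; 180 randomised per arm, 126 of them with a 6-month weight if nobody is removed
- r = share of the coached arm removed
- q = share of removed women who would otherwise have given the weight: 70% (the planned follow-up) or 35% (half of it)
- d = excess retention of removed women over the others, 1 to 5 kg
- removal before any postpartum weight, and no help from the baseline weight in predicting the excess

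Formulas:

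- weights lost = 180 × r × q
- f = lost/126 = r × q/0.70
- bias = f × d
- SE = 7 × √(1/126 + 1/(126 × (1 − f)))
- type I error = P(|Z + bias/SE| > 1.96)

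| r (women) | q | f | SE (kg) | Bias, d = 1 to 5 (kg) | Type I error |
|---|---|---|---|---|---|
| 2% (about 4) | 35% | 1% | 0.884 | 0.01–0.05 | 5.00–5.04% |
| 2% (about 4) | 70% | 2% | 0.886 | 0.02–0.10 | 5.01–5.15% |
| 5% (9) | 35% | 2.5% | 0.888 | 0.025–0.125 | 5.01–5.23% |
| 5% (9) | 70% | 5% | 0.893 | 0.05–0.25 | 5.04–5.90% |
| 10% (18) | 35% | 5% | 0.893 | 0.05–0.25 | 5.04–5.90% |
| 10% (18) | 70% | 10% | 0.906 | 0.10–0.50 | 5.14–8.55% |

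At d = 4 kg, type I error passes 6% only at f = 6.6% (bias 0.26 kg). That means about 12 women removed at q 70%, or 24 at q 35%. For r = 5%, q = 70% and d = 5 kg, it runs from 6.5% (SD 5.5) to 5.6% (SD 8.8) across the SDs in Table 6.

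**Step 4. Later removal.** Assume correlations of 0.85 between adjacent visits and 0.72 between months 2 and 6, and an excess that builds as 1/3, 2/3 and all of 4 kg. With f = 5% the bias is:

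- 0.05 × 4 = 0.20 kg before any postpartum weight
- 0.20 × (1 − 0.72/3) = 0.15 kg after the 2-month weight
- 0.20 × 0.431 = 0.09 kg after the 4-month weight (regression slopes −0.009 and 0.858)

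If the full excess already shows at 2 months, the last two become 0.20 × 0.28 = 0.06 kg and 0.20 × 0.151 = 0.03 kg.

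**Step 5. Opposite direction.** With nobody removed, power at 2.87 kg is Φ(2.87/0.882 − 1.96) = 90.2%. With r = 5%, q = 70% and removed women 3 to 5 kg below the others, it is Φ((2.87 − 0.15)/0.893 − 1.96) = 86.1% to Φ((2.87 − 0.25)/0.893 − 1.96) = 83.5%.

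**The case against.** The strongest reply is that the rule may hardly ever be used. It is permissive. Section 12.1.e answers missed coach calls with outreach through home visitors. Section 12.2 plans to relate fidelity to the weight outcome, which fits better with keeping low-adherence women than with removing them. Table 1 requires willingness to give home weights, and section 8.2 requires one valid scale weight before randomisation, so some likely non-compliers never enter. The planned 30% loss may already count some removals. Section 10 mentions manuals of operations, which are not among the documents and could settle the matter. All of this stands and lowers the likely size. None of it supplies the missing protection in the protocol.

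A second reply is that women who ignore the intervention might give no 6-month weight anyway, since weekly weighing is part of it. That is fair. It makes q = 70% an upper case and is why 35% is shown beside it. The excess of 1 to 5 kg has no source in the documents, and its lower end gives almost no bias.

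A third reply is that the mixed model handles missing data. It removes the part of the bias that earlier weights explain (step 4), but it need not remove the rest.

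A reader might also fault the section 15.2 model for having no adherence term. That does not follow: an intention-to-treat model would not normally adjust for adherence after randomisation.

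**Conclusion.** The point holds as a gap between the discontinuation rule and the analysis aim. Followed as written, section 14.1 can lose primary outcomes for an adherence-related reason, mainly in one arm, and sections 14.0, 14.2 and 15 do not clearly prevent it. Under the stated assumptions the bias is negligible at 2% removed, about 0.03 to 0.25 kg at 5% (type I error 5.0% to 5.9%) and 0.05 to 0.50 kg at 10% (5.0% to 8.6%). Later removal makes it smaller. These figures illustrate the mechanism; they are not a forecast.

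Two stronger readings are not supported. A reader might infer that the trial will favour H42-HV. The documents give no removal rate and no direction, and the opposite direction costs power instead (90.2% to about 86%–83% in step 5). A reader might also infer that non-adherent women are excluded from the analysis, or that only the coached arm is exposed. Section 15.2 keeps all randomised women in the model, and the disruptive-behaviour half of the same ground can arise in either arm. This is a cheap improvement, held with medium confidence.

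**What to change.** Reconcile sections 14.0 to 14.2 on discontinuation and withdrawal with sections 15.1 and 15.2:

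- State that discontinuation for intervention non-compliance does not by itself end outcome follow-up.
- Unless the participant declines, or another section 14.1 ground also applies, still seek the 2-, 4- and 6-month home-scale weights at their scheduled dates and analyse them as randomised.
- Record any weight taken at early discontinuation under its actual date, never as the 6-month value.
- Report investigator discontinuations by arm and reason. Reasons are already documented under sections 14.0 and 14.2, so only the tabulation by arm is new.

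Decisions on when coaching stops, and the best-interest, harm and disruptive-behaviour grounds, stay with the investigators. A case that mixes non-compliance with one of those grounds falls outside the change.

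The cost is protocol wording plus some extra reminder contact with women no longer being coached. The scale is already in the home and transmits by itself (section 9.2, Assessment of maternal weight using the Home Scale). If follow-up stays at the planned 70%, Table 6 is unchanged. The wording is best settled before the rule is used, because a 6-month weight that was not sought cannot be recovered later.
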